Specific Aim 1 will assess if patients with asymptomatic carotid stenosis differ in cognitive function compared to age-matched controls without carotid stenosis but with similar vascular risk profiles. We hypothesize that in patients with asymptomatic carotid stenosis $\geq 50\%$ who survive stroke free for 2 years; the change in overall and domain-specific cognitive function will be significantly different compared to those without stenosis. The study will recruit 284 subjects and will detect a clinically significant difference in cognitive score with 90% power. We will use a novel battery of cognitive tests specifically developed to address the unique issues relating to carotid stenosis.

Specific Aim 2 will define plaque-morphometric, biologic, and hemodynamic characteristics that correlate with cognitive impairment in patients with asymptomatic carotid stenosis. We hypothesize that carotid plaque architecture, plaque composition, microembolic counts, serum pro-inflammatory markers, and cerebral hypoperfusion could each mediate cognitive decline over a 2-year follow-up period. We will implement a novel clinical 3D B-mode ultrasound imaging technique developed to obtain reliable serial plaque measurements.

Specific Aim 3 will measure the impact of cognitive impairment on quality of life. We hypothesize that at 2 years, regardless of plaque features, cognitive impairment will correlate with a reduction in health-related quality of life measures.

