Specific Aim 1 of the study will assess whether in patients with asymptomatic carotid stenosis $\geq 50\%$ who survive stroke-free for 2 years, change in overall and domain-specific cognitive function will be significantly different compared to those without stenosis. We will confirm the group distribution of demographic variables.

Additional analyses will be performed after correction for the age, education and mood status of patients. This hypothesis will be examined with analysis of covariance comparing the composite change scores for patients versus non-stenosed control groups at the 2-year time point after adjustment for the baseline cognitive function score. Although we anticipate the level of missing data due to missed visits to be modest, these analyses will be conducted using the mixed modeling approaches of Laird and Ware.

Specific Aim 2 (a through d) is designed to identify potential mechanisms of cognitive change in patients with asymptomatic carotid stenosis. We hypothesize that carotid plaque architecture, plaque composition, microembolic counts, serum pro-inflammatory markers, and cerebral hypoperfusion could each mediate cognitive decline. Within this aim, there are 2 hypotheses for each mechanism:

A) At 2 years, the features listed above will independently predict a change in cognitive function. The statistical approach for this aim will be identical to that of the hypothesis in specific aim 1. Associations with cognitive

change scores and plaque area, volume, composition, microembolic counts, serum pro-inflammatory marker levels and cerebrovascular reactivity will be assessed using the mixed models of Laird and Ware106. Power to detect associations of cognitive decline with each of these features can be estimated using the same approaches as for the hypothesis in aim 1. We have used the most conservative approach of dichotomizing these continuous variables at their median value – the actual analysis will be performed using the variables as continuous measures where the power will be greater. Using this very conservative approach for power calculations, the same detectable differences in change score of 0.4 SD with 90% power, and of 0.3 SD with 80% power, are achievable.

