Practice effect on cognitive testing. Since patients will be exposed to the same cognitive tests at different periods, scores may improve due to the “practice effect.” In this study, the practice effect is anticipated to be low since tests are being repeated at 1 year intervals (baseline, 1 year, and 2 years post-recruitment). Alternate test forms will be used wherever possible. Reliable change analyses will be used to determine if changes detected in the composite score, as well as on specific domain scores of interest exceed that which is expected based on repeated exposure to the measure, error variance, and maturation.

Additional analysis of Aim 1 including patients with post-recruitment stroke. Based on prior randomized trials, it is anticipated that approximately 1-2% of our patients per year will suffer a stroke2. Separating primary cognitive deficits from poor performance on cognitive testing due to disability associated with stroke is difficult. Furthermore, patients that develop stroke during follow-up will require carotid revascularization with elimination of the stenosis per standard of care. That is why the proposed study will exclude such patients when evaluating cognitive outcome. This attrition has been accounted for in the power analysis, and will not affect our results. Moreover, for those unable to complete testing due to stroke, the statistical E-M algorithm (Laird and Ware106) will be used to provide an estimate of the mean score in the presence of the missing data. This statistical approach has been shown to produce unbiased estimates that are more precise than alternative approaches in the presence of data that are missing.

Additional analysis of Aim 1 comparing baseline cognition in the two groups. We feel that a major strength of the application is the longitudinal data collection and comparisons of change scores. This is statistically much more powerful than a simple cross-sectional comparison. However, we will have data on baseline cognitive scores for patients versus control subjects. In an additional analysis we will perform a simple comparison of these scores to measure differences at baseline in the two populations.

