Additional analysis of Aim 2 focusing on correlations with stroke during follow-up. For the patients in the cohort that suffer a stroke during follow-up, we will have plaque architecture, plaque composition, microembolic count, pro-inflammatory marker, and perfusion information, prior to their stroke. We are aware of the fact that the focus of our study is not on stroke; furthermore, these 5 to 10 patients will be too few to derive statistically strong conclusions. However, we will analyze available data and report additional conclusions on plaque correlates of stroke, if the information is hypothesis-generating.

TCD microembolic counts. We are aware that automated emboli counts and classifications are subject to the effectiveness of signal filtering algorithms. Therefore filters will be programmed according to criteria validated in consensus documents70. As an added precaution, we will analyze all spectral recordings manually to confirm embolic counts.

Temporal consistency. We are aware that the significance of outcomes and interpretation of mechanisms may be influenced by differential temporal effects. While the primary statistical approach will be to evaluate change scores over 2 years; we will describe the temporal pattern of cognitive changes and assess if the hypotheses are temporally consistent at the 1-year time interval.

Vascular risk factor distribution. We realize that the control group will include patients with a heterogeneous mix of one or more vascular risk factors. It is likely that one risk factor may have a larger influence on cognitive function than another; or multiple risk factors together in a patient may influence cognition more than in a patient with one risk factor. However, in a study of this size with finite resources, it will not be possible to expand the control group to the large numbers required to study the effects of each risk factor alone and in various combinations. In any case, that is well beyond the focus of this investigation. We will closely monitor the control subjects to ensure no unusual heterogeneity of cognitive scores. If such is found, we will then focus on recruiting patients with limited (one or two) risk factors alone.

**With regards to the planned additional follow-up, we will perform standard correlation analyses between cognitive scores of the subjects obtained previously with physical function scores that we plan to obtain during the additional follow-up.

ID: VIEW4E02806052800

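### In the available text, no Aim 1 analysis names a vascular risk factor as a covariate, although this non-randomised comparison depends on similar vascular risk in the two groups

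*Combined protocol and SAP*

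**What the plan says.** The premise is in Justification, Objective, & Research Design, item 1: Aim 1 uses "age-matched controls without carotid stenosis but with similar vascular risk profiles". Item 2 of the same section repeats it. Assignment is by disease status, not by randomisation.

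The analysis is in Sample Size and Data Analysis, item 2:

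- **Main model:** an ANCOVA, described as "comparing the composite change scores for patients versus non-stenosed control groups at the 2-year time point after adjustment for the baseline cognitive function score", fitted with mixed models.
- **Further adjustment:** "Additional analyses will be performed after correction for the age, education and mood status of patients".
- **Balance check:** "We will confirm the group distribution of demographic variables".
- **Baseline contrast:** "In an additional analysis we will perform a simple comparison of these scores to measure differences at baseline in the two populations".

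The paragraph on vascular risk factor distribution accepts that the control group will be mixed and adds: "It is likely that one risk factor may have a larger influence on cognitive function than another". Its response is "We will closely monitor the control subjects to ensure no unusual heterogeneity of cognitive scores", followed by "If such is found, we will then focus on recruiting patients with limited (one or two) risk factors alone". It names no adjustment.

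Aim 3, on quality of life, does plan to control for medical co-morbidities. Aim 1, which carries the primary hypothesis, does not.

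**The concern.** A non-randomised comparison can be read as an effect of stenosis only if the groups are alike in other causes of cognitive change, or if the analysis allows for the differences. The plan itself says that vascular risk factors probably influence cognition. If they also differ in frequency between the groups, part of the Aim 1 difference would be credited to stenosis. Adjusting for baseline cognition may absorb effects already present at entry. It may not fully remove a continuing effect on the rate of change, and 2-year change is the outcome. The planned balance check would not show the problem, because it is limited to demographic variables.

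**Working it through.** **1. The plan's own figure.** Inputs: 142 per group and a detectable difference of 0.4 SD at 90% power (Sample Size and Data Analysis). Neither alpha nor sidedness is stated for Aim 1; I assume 5% two-sided.

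- Standard error of the difference = sqrt(2/142) = 0.119 SD.
- Noncentrality = 0.4/0.119 = 3.37, df 282.
- Power = 91.9%, consistent with the stated 90%. The point does not dispute this figure.

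**2. Do the entry rules secure similar risk?**

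- Controls (Research Related Risks): at least one of hypertension, diabetes, smoking and prior cardiovascular disease. Number and type are otherwise free.
- Stenosis patients (Eligibility): asymptomatic stenosis of 50% or more. There is no risk-factor criterion.
- Non-veterans (VA-Specific Criteria, item 2.1): an age and risk range like that of veterans. This compares non-veterans with veterans, not patients with controls.

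So there is a floor for one group, none for the other, and no visible procedure that matches on number or type of factors.

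**3. Possible size.** The documents give no risk-factor frequencies by group and no effect on change, so every input here is an assumption.

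Bias = (effect per factor on 2-year change) x (between-group gap in mean factor count), with effects of 0.05 and 0.20 SD, gaps of 0.25 and 0.5, and no absorption by the baseline score:

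- 0.05 x 0.25 = 0.0125 SD
- 0.05 x 0.5 = 0.025 SD
- 0.20 x 0.25 = 0.05 SD
- 0.20 x 0.5 = 0.10 SD

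With no true stenosis effect, the rejection rate comes from a noncentral t with noncentrality = bias/sqrt(2/n) and df = 2n - 2:

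| n per group | 0.0125 | 0.025 | 0.05 | 0.10 |
|---|---|---|---|---|
| 142 | 5.1% | 5.5% | 7.0% | 13.4% |
| 128 (10% loss) | 5.1% | 5.5% | 6.8% | 12.5% |
| 114 (20% loss) | 5.1% | 5.4% | 6.6% | 11.7% |

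**4. Power cost of adjusting.** The model has eight covariates: baseline cognition, age, education, mood and the four factors. Noncentrality = 0.4/sqrt((2/n)/(1 - R2)), where R2 is the assumed share of group membership that the covariates explain. With intercept and group, df = 2n - 10.

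| n per group | R2 = 0 | 5% | 10% | 15% |
|---|---|---|---|---|
| 142 | 91.9% | 90.6% | 89.0% | 87.2% |
| 128 | 89.0% | 87.4% | 85.6% | 83.6% |
| 114 | 85.2% | 83.4% | 81.4% | 79.2% |

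These figures ignore any gain from lower residual variance. The loss rates are assumptions, but some loss is likely: patients leave the study on stroke, TIA or revascularisation.

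**The case against.** **The missing detail may exist elsewhere.** Study Procedures, item 1, refers to tables on page 32 of a protocol. The Research Protocol page lists a file, ACCOF - revised 2-14-11, and Eligibility lists a control checklist. None of these is shown, and the method of age matching is not visible either. The Research Protocol page does say that the application itself carries the study information, but the page 32 reference shows that it also relies on another document. This objection stands as a limit: a reader might infer that the study has no risk-factor matching or adjustment at all, and the documents do not support that.

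**Similarity may be good in practice.** Patients come from vascular clinics and laboratories, after a bruit or work-up for other vascular disease. Those free of all four factors are probably uncommon. This weakens the missing floor for patients, but it does not balance the number or type of factors.

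**The planners saw the issue.** They did, but they declined to study each factor and combination separately because that needs a larger control group. Covariate adjustment does not. Their contingency depends on control cognitive scores, not on imbalance between groups. A reader might infer that it excludes later controls with three or four factors. The text speaks of a recruitment focus, and nothing shows that it was ever used.

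**The size is assumed.** True. Larger inputs, such as a gap of one whole factor at 0.20 SD per factor, give a bias of 0.20 SD and an error of 39%. The documents support neither that figure nor a claim that confounding would produce the 0.4 SD target difference.

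**Conclusion.** The point holds for the text available. The stated covariates for Aim 1 are baseline cognition, then age, education and mood. The entry rules do not guarantee the similar vascular risk on which the comparison rests, and the plan accepts that such risk probably affects cognition. Following the stated list could leave the group difference confounded.

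The direction of any bias is unknown. Under the assumptions shown, its effect runs from negligible to modest, and at the low end the test keeps essentially its nominal error. This should be corrected because the correction is cheap. It does not show that an Aim 1 difference would be spurious. Confidence is medium, because the unseen protocol or checklist could settle the matter; if either already specifies the adjustment, a cross-reference is enough.

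**What to change.** First confirm that all four factors were recorded with the same definitions in both groups. Study Procedures, item 1, lists the vascular risk profile for patients and names only ultrasound and cognition for controls, although control entry depends on these factors.

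Then amend Sample Size and Data Analysis, item 2:

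1. Add a dated, adjusted Aim 1 model with hypertension, diabetes, smoking and prior cardiovascular disease alongside baseline cognition, age, education and mood. Report it beside the planned model, and base any attribution to stenosis on the adjusted estimate. State whether between-group results had been seen by that date, since Monitoring Plan - Individual provides for review of outcomes and preliminary analyses during the study. If they had, label the model post hoc.
2. Extend the balance check to each risk factor by group, with standardised differences.
3. As a sensitivity analysis, omit prior cardiovascular disease. Its definition includes coronary and peripheral arterial disease, so adjusting for it may be over-adjustment.

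The cost is plan wording, one data check, a table and two model fits, plus the modest power loss shown above. Because recruitment has closed, a model added now also carries some risk of analytic flexibility. Dating it and reporting both models limits that risk.

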Asymptomatic carotid stenosis affects 2-12% of people. With 23.4 million veterans in the country, at least 1 million (4.3%) have asymptomatic carotid stenosis and are at risk for cognitive impairment. A subset analysis of the Cardiovascular Health Study found cognitive decline in 34% of 32 patients with asymptomatic carotid stenosis. In this proposal, we will define the extent of initial and progressive cognitive impairment in veterans with carotid stenosis who are currently labeled as "asymptomatic" in the absence of a focal neurologic deficit (stroke, transient ischemic attack). Programs to prevent, postpone, or mitigate cognitive impairment in patients with carotid stenosis will depend on the identification of mediators for cognitive impairment. Microembolic brain injury and cerebral hypoperfusion have been associated with cognitive impairment in elderly individuals. Therefore plaque architecture, plaque composition, microembolic counts, serum inflammatory markers, and cerebral hypoperfusion are likely mediators of impaired cognition in patients with asymptomatic carotid stenosis. As part of this proposal, we will identify the biological mechanisms by which carotid stenosis could result in cognitive impairment.

BACKGROUND AND SIGNIFICANCE

The magnitude, determinants, and functional impact of cognitive impairment associated with carotid stenosis have not been evaluated. In the first study of its kind, we

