B) At 2 years, patients with asymptomatic carotid stenosis who develop cognitive impairment will differ in these characteristics compared with similar patients that remain unchanged. The differential mean value for plaque area, volume, composition, microembolic counts, serum pro-inflammatory marker levels and cerebrovascular reactivity will be tested between the two groups using t-tests. The detectable difference for each of these factors is again very conservatively estimated to be the same differences of 0.4 SD with 90% power, and 0.3 SD with 80% power (now the SD of each of these factors). Such a small change relative to the SD of each of these factors is reasonable to define as being small enough to detect all “clinically important changes.”

Specific Aim 3 is designed to explore whether cognitive changes in patients with asymptomatic carotid stenosis correlate with changes in health-related quality of life. We hypothesize that at 2 years, regardless of plaque features, cognitive change will correlate with change in health-related quality of life measures.

For this aim, the principal outcome variables will be the change in quality of life measures (Frenchay and SF-36) between baseline and follow-up. The outcome event will be cognitive change score at the corresponding follow-up time point. Initially, the correlation between each quality of life change score and corresponding cognitive change score will be explored in a univariate fashion using t-tests. Subsequently, multivariate analysis will be used to determine the independent impact of altered cognition on quality of life after controlling for additional patient variables such as age, gender, mood, medical co-morbidities, and degree of stenosis. Independent predictors of change in quality of life will be selected based on $p \leq 0.05$. With the sample size of 142, a correlation of 0.2 between change in cognitive function and change in quality of life can be detected with 90% power, and a correlation of 0.18 can be detected with 80% power.

Potential difficulties and Alternate approaches/analyses:

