** With regards to the planned additional follow-up, all subjects enrolled in ACCOF will be contacted directly to gauge their interest in participating. There is no script being used to recruit these subjects other than information contained in the informed consent.

2 * Describe measures that will be implemented to avoid participant coercion or undue influence (if not applicable to the study,

enter "N/A"):

The study purpose, procedures, risks and benefits will be explained to the patient. An evaluation to sign consent form will be used to determine the mental eligibility of the consenting individual. If the subject answers more than one question incorrectly he will be disqualified.

** With regards to the planned additional follow-up, the same procedure will be followed.

3 * Who will recruit participants (or acquire charts/records/samples) for this study? (Check all that apply)
Study Staff

3.1 If you are using a third party, specify Third Party Recruiters:

4 Upload any recruitment tools such as screening/telephone scripts and introductory letters (do not upload advertisements here):

Name	Created	Modified Date
------	---------	---------------

There are no items to display

ID: VIEW4E0BCAA0A6C00
Name: v2_Recruitment

View: v2_Advertising

Advertising

1 * Will you be using advertisements to recruit potential participants?

Yes No

ID: VIEW4E0BCCF811000
Name: v2_Advertising

View: v2_Research Related Risks

Research Related Risks

If you uploaded a separate research protocol document in the 'Research Protocol' page, cite the applicable section and page numbers from that document in the answer box below.

1 * Individually list each research-related risk, using a separate line for each. Next to each risk, delineate the likelihood/seriousness of the risk, and the provisions for minimizing the risk:

Original ACCOF protocol:

Risks to subjects

Human subjects' involvement and characteristics. This study will involve 142 adult patients with asymptomatic carotid artery stenosis, and 142 adult subjects without carotid stenosis but with one or more vascular risk factors (hypertension, diabetes, prior cardiovascular disease, or smoking). No patients with a prior stroke, pregnant women, prisoners or children will be included. The vulnerability of the study population will be limited to the fact that they are patients with a risk for stroke.

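### Aim 2B tests a mechanism hypothesis with unadjusted t-tests between outcome-defined groups, so a shared cause such as age can produce a feature difference

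*Combined protocol and SAP*

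**What the plan says.** Sample Size and Data Analysis, item 2, gives two hypotheses for each candidate mechanism in Specific Aim 2.

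- **Hypothesis A** asks whether the features independently predict cognitive change. On method: "The statistical approach for this aim will be identical to that of the hypothesis in specific aim 1". Aim 1 is an analysis of covariance adjusted for baseline cognitive score, fitted by mixed models. It adds: "Additional analyses will be performed after correction for the age, education and mood status of patients".
- **Hypothesis B** compares patients who become impaired over 2 years with those who do not: "patients with asymptomatic carotid stenosis who develop cognitive impairment will differ in these characteristics compared with similar patients that remain unchanged". On method, the means of the plaque measures, microembolic counts, "serum pro-inflammatory marker levels and cerebrovascular reactivity will be tested between the two groups using t-tests". No covariate, matching or stratification is named. The research design section and Study Procedures, item 2, repeat the hypothesis without adding a method.

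Aim 3 also starts with univariate tests, but then moves to a multivariable model that includes age, gender, mood, co-morbidities and degree of stenosis. Hypothesis B has no such second step.

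**The concern.** Aim 2 exists to identify mechanisms of cognitive change. Hypothesis B splits the stenosis cohort by what happened to cognition and then looks back at the features. Nothing in that split balances age, education, mood, starting cognition or vascular risk. The entry age is simply 18 or older, and the age-matching described under Aim 1 concerns patients against stenosis-free controls, not impaired against unchanged patients.

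If older patients decline more and also have larger plaques or higher inflammatory markers, the t-test will tend to show a feature difference even when the feature plays no part in decline. At stake is whether a positive B result can be read as evidence for a mechanism. The same few background variables could act on several of the listed features at once, so several positive t-tests would not be independent support.

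**Working it through.** **The plan's own figure for B.** The detectable differences are "again very conservatively estimated to be the same differences of 0.4 SD with 90% power, and 0.3 SD with 80% power". For two means with SD 1, two-sided 0.05, power ≈ Φ(d/SE − 1.96), with SE = √(1/n₁ + 1/n₂).

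| Groups | SE | Power, 0.4 SD | Power, 0.3 SD |
|---|---|---|---|
| 142 v 142 | 0.119 | 92% | 71% |
| 71 v 71 | 0.168 | 66% | 43% |
| 48 v 94 | 0.177 | 62% | 39% |

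The stated figures do not reproduce for a cohort of 142 split in two. They resemble a 142 v 142 comparison, though even that gives 71%, not 80%, for 0.3 SD. This is a separate problem, and the present point does not depend on it.

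**Inputs for the confounding check.**

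- Cohort: "This study will involve 142 adult patients with asymptomatic carotid artery stenosis" (Research Related Risks, item 1).
- Share impaired: not given for B. The one figure in the documents is that a cited subset analysis "found cognitive decline in 34% of 32 patients with asymptomatic carotid stenosis" (Justification, Objective, & Research Design, item 4). 34% of 142 is 48, leaving 94. This is an assumption.
- Correlations of the confounder with the feature (r₁) and with decline (r₂): not in the documents, so a range is used.
- No direct link between feature and decline; two-sided 0.05, which the plan does not state for B.

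**Step 1: spurious difference.** If the impaired group is the top p = 48/142 = 0.338 on a normal latent decline scale, the groups differ on that scale by φ(z)/[p(1 − p)], with z = 0.418 and φ(z) = 0.366. That is 0.366/(0.338 × 0.662) = 1.63 SD. The feature then differs by r₁ × r₂ × 1.63 SD.

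**Step 2: false-positive rate.** With SE = √(1/48 + 1/94) = 0.177 and λ = difference/SE, the rate is Φ(λ − 1.96) + Φ(−λ − 1.96). At 0.3 and 0.3: difference = 0.09 × 1.63 = 0.147; λ = 0.147/0.177 = 0.83; rate = 0.129 + 0.003 = 13.2%.

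**Step 3: comparison with simulation** (4,000 simulated studies per setting, n = 142; where two values are shown, they come from two separate simulations).

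| r₁ / r₂ | Spurious difference | Closed form | Simulated t-test | Simulated, confounder in model |
|---|---|---|---|---|
| 0 / 0 | 0 | 5% | 5.1% | 5.0% |
| 0.2 / 0.2 | 0.07 SD | 6.6% | 6.8%, 7.1% | 5.1%, 5.4% |
| 0.3 / 0.3 | 0.15 SD | 13.2% | 12.5%, 13.1% | 4.7%, 4.4% |
| 0.4 / 0.3 | 0.20 SD | 19.7% | 19.8% | 4.6% |
| 0.4 / 0.4 | 0.26 SD | 31.4% | 31.0% | 5.4% |
| 0.5 / 0.5 | 0.41 SD | 63.4% | 64.5% | 5.1% |

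An equal split gives much the same: 7.2%, 14.1%, 32.6% and 67.6% at 0.2/0.2, 0.3/0.3, 0.4/0.4 and 0.5/0.5. All rates are per test. The inflation is slight at 0.2/0.2 and becomes material from about 0.3/0.3.

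**The case against.** **Hypothesis A already asks for independent prediction.** This is the strongest reply, and it stands in part. A uses the features as continuous variables and inherits the Aim 1 approach, with its additional correction for age, education and mood. Still, B is a separately stated hypothesis with its own test and its own power statement, and nothing makes its interpretation conditional on A.

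**The word 'similar' promises nothing.** A reader might infer that B undertakes to compare matched or otherwise balanced patients and then fails to do so. The documents do not support that. The phrase most naturally means other patients in the same asymptomatic stenosis cohort. Eligibility also narrows the range: stenosis of at least 50%, no earlier stroke or TIA, no occlusion and no scheduled revascularization, with revascularization usually considered only above 80%. That restriction is real, but it does not balance age or risk factors between outcome groups.

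**Age may already be handled.** The tests have age norms, and the practice-effect paragraph says reliable-change analysis allows for maturation. Either could weaken the link between age and decline. The plan does not say that either defines the B groups.

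**Other analyses are unadjusted too.** True: the baseline comparison of patients with controls and the follow-up correlations have no covariates. It would be wrong to say that B alone lacks them. Among the hypotheses under the three numbered aims, however, B is the one whose planned analysis ends with an unadjusted test.

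**Adjusting for stenosis could remove the signal.** This stands. Plaque area is taken at the region of maximum stenosis, and Study Procedures describes hypoperfusion as associated with the stenosis. Degree of stenosis is a named covariate nowhere in Aim 2, so it is not a gap peculiar to B, and it should not be forced into every model.

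**Conclusion.** The point holds: B tests a mechanism hypothesis by unadjusted comparison of outcome-defined groups, and a shared cause such as age can produce the difference it looks for. The false-positive rate per test is about 7%, 13% and 20% at correlations of 0.2/0.2, 0.3/0.3 and 0.4/0.3, against about 5% with the confounder in the model. These figures rest on assumed correlations, an assumed 34% impaired and a single, fully measured confounder. They show that the bias can matter, not that it is present.

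A reader might infer that a confounded B result would by itself be reported as a mediator. The documents do not say so, because A stands beside it. Nor do they show that patients who decline are older or have more severe stenosis. The change is worth making because it is cheap and brings B into line with the adjustment already planned for Aims 1 and 3. B is secondary to Aim 1, and its weakness does not touch the primary comparison.

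**What to change.** For each feature, make the main B analysis a pre-specified linear regression of the feature, on its chosen scale, on cognitive-course group (impaired or unchanged). Covariates: age, education, mood, baseline cognitive score and the recorded vascular risk factors. Report the adjusted mean difference with its confidence interval. Keep the t-test as a descriptive result.

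Add degree of stenosis only as a sensitivity analysis, showing results with and without it. State the reason in the SAP: it is closely tied to plaque area and volume, and it may lie on the pathway to reactivity.

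**Cost.** A few degrees of freedom, slightly more analysis and a paragraph of SAP wording. Demographics, risk factors, cognition and stenosis are already recorded, and education and mood are already planned Aim 1 covariates. The questionnaire list names no mood scale, so the SAP should say which measure supplies that covariate. If impairment turns out to be rare, the covariate list should be kept short.
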